Arm 1: This study has been modified to explore one veledimex dose in Arm 1: 10 mg.

Arm 2: This study is designed to explore two veledimex doses in Arm 2: 10 mg and 20 mg. Subject enrollment and veledimex dose escalation will proceed according to a standard 3+3 design. The first cohort will receive 10 mg veledimex followed by the second cohort receiving 20 mg veledimex.

Arm 1 and Arm 2 subjects may exhibit different safety and tolerability profiles. The 3+3 standard study design has been modified to independently evaluate the two arms separately.

The study arms and assigned doses will be divided into 3 cohorts as shown below:

Table 4a: ATI001-103 Cohorts

Arm	Cohort	Indication	Procedure	Assigned Veledimex Dose ^a
1	1	Resectable pediatric brain tumor	Craniotomy	10 mg
2	3 ^b	DIPG	Stereotactic	10 mg
2	4	DIPG	Stereotactic	20 mg

^a Doses are BSA-adjusted doses

^b Arm 1 Cohort 2 was removed in Protocol Amendment 2. The SRC reviewed the safety profile of Arm 1 Cohort 1 and determined it was appropriate to move forward with Arm 1, Cohort 2 and Arm 2, Cohort 1, however due to issues with enrollment of supratentorial patients, it was determined not to proceed with Cohort 2.

Note: After the completion of a phase I dose escalation cohort in Arm 2, the SRC may elect to expand that cohort by up to 30 DIPG patients, which will be considered the Phase II component of study.

Each cohort will consist of subjects \leq 21 years-of-age who meet eligibility criteria.

Each subject in each dose escalation cohort will be monitored for 28 days after Ad-RTS-hIL-12 injection before additional subjects are enrolled in the same cohort. The evaluation period for DLT is 28 days after Ad-RTS-hIL-12 injection (Day 0 to Day 28).

Determination of safety and the recommendation to expand the current dose cohort, dose escalate, or discontinue the investigation, will occur after all dosed subjects in a cohort have been evaluated for at least 28 days after Ad-RTS-hIL-12 injection, as described in Section 7.3.

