7.4. Dose-Limiting Toxicity

An event, occurring within the first 28 days (*i.e.*, Day 0 to Day 28) that meets at least one of the following conditions:

- Any local reaction that requires operative intervention and is felt to be attributable to study drug
- Any local reaction that has life-threatening consequences requiring urgent intervention or results in death and is felt to be attributable to study drug
- Any Grade 3 or higher non-hematologic adverse event that is at least possibly related to study drug and lasts ≥ 3 days
- Nausea and vomiting will not be considered a DLT unless at least Grade 3 or 4 and refractory to antiemetics (*i.e.*, defined as symptoms unrelieved by maximal medical support as directed by the PI (per institutional guidelines) in consultation with the medical monitor).
- Grade 3 or higher thrombocytopenia ($< 50,000/\text{mm}^3$) at least possibly related to study drug

- Any Grade 4 or higher hematologic toxicity (except thrombocytopenia) that is at least possibly related to study drug and lasts ≥ 5 days

Dose escalation may be stopped by the Medical Monitor before a DLT is observed, but where the observed toxicities indicate the strong likelihood of unacceptable toxicity at higher doses.

Note: Diagnostic brain tumor biopsy is not considered a DLT. Seizures, headaches, and cerebral or pontine edema are commonly observed in this population and will be recorded according to the grade of toxicity but will not be considered a DLT unless a relationship to study drug is deemed to be the main contributory factor. Transient neurological changes are expected in Arm 2 and will not be considered a DLT unless they last > 10 days.

Expansion cohorts will be allowed in Arm 2 if deemed appropriate by the SRC. If an expansion cohort is implemented, the veledimex dose may be delayed or reduced for individual subjects in the event of toxicity. If $\geq 33\%$ of subjects in the expansion cohort experience DLTs, using the definition in the dose-escalation phase, additional subjects may be enrolled at the next lower dose tested in the dose-escalation phase or at an intermediate dose, as recommended by the SRC. All DLTs should be reported to the Sponsor within 24 hours of Investigator/site awareness.

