7.6. Dose Modification and Dose Delays

Treatment dose delays and dose reductions for individual subjects will be allowed in the event of toxicities, according to the criteria shown in [Table 6](#). If a drug-related Grade 3 or higher AE occurs (excluding nausea and/or vomiting in subjects who did not receive optimal treatment with anti-emetics), the Investigator in conjunction with the Sponsor's Medical Monitor will decide whether the subject will remain on the study. The withheld doses will not be made up; the subject may be allowed to complete dosing according to the remaining schedule.

As mentioned in [Section 7.4](#), fatigue, seizures, headaches, and cerebral or pontine edema are commonly observed in this population and will be recorded according to grade of toxicity, but

will not be considered a DLT unless a relationship to study drug is deemed to be the main contributory factor. If $\geq 33\%$ of subjects experience DLTs, the SRC will convene to determine the course of action. The Medical Monitor or Investigators may request a meeting of the SRC at other times, as deemed clinically indicated.

Table 6: Criteria for Dose Delay and Dose Reduction

Event	Course of Action
Any local injection reaction that requires operative intervention	Hold study drug and contact the Medical Monitor for instructions on resuming dosing
Any local injection reaction that has life-threatening consequences requiring urgent intervention or results in death	Hold study drug and contact the Medical Monitor for instruction on resuming dosing
Any drug-related Grade 3 or higher AE ^a	Hold study drug and contact the Medical Monitor for instruction on resuming dosing

^a Excluding nausea and/or vomiting in subjects who did not receive optimal treatment with anti-emetics

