8.5. Replacement of Subjects

Subjects who withdraw from the study during the DLT evaluation period (Day 0 to Day 28) for reasons other than toxicity or disease progression may be replaced.

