16.1. Populations for Analysis

This is an amendment to an ongoing study that has been previously described. For all practical purposes the connotation of the safety population for the planned safety analysis are subjects being denoted in defining the overall safety population (OSP) defined below to distinguish this group from the subgroup of subjects denoted as the evaluable safety population (ESP) who must receive Ad-RTS-hIL-12 and at least one dose of veledimex after injection.

This distinction provides for inclusion of both drug components (Ad-RTS-hIL-12+ veledimex) in order to evaluate dose escalation via the rule-based criteria fundamental to the 3+3 method. This means that during dose escalation if at least one of three Ad-RTS-hIL-12 treated subjects does not receive at least one dose of veledimex, additional eligible subjects will be enrolled as applicable in order to achieve the samples size of three evaluable subjects to assist the SRC's evaluation when making a dose escalation or a dose de-escalation decision. Specifically,

- The OSP will be used to perform safety evaluations for all subjects who have received at least one dose of veledimex or Ad-RTS-hIL-12.
- The ESP will include subjects who received Ad-RTS-hIL-12 and at least one dose of their cohort specific-dose of veledimex after Ad-RTS-hIL-12 administration and are BSA conformant. The ESP will be used to make decisions regarding escalation to higher veledimex doses for Arms 1 and 2 separately, based on a standard 3 + 3 design, as described in [Section 7.3](#).
- The Pharmacokinetics Population (PKP) for veledimex includes all subjects who receive veledimex with sufficient PK timepoints.

Up to 30 evaluable subjects in the Phase II expansion cohort may be enrolled to provide time to OS estimation. This subgroup will include subjects treated with both Ad-RTS-hIL-12 and at least one dose of veledimex as defined by the ESP and other evaluability criteria described in the Statistical Analysis Plan.

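### In Arm 2 a child can count as DLT-free in the 3+3 after one of 14 veledimex doses, and no rule says how a child who leaves before Day 28 is counted

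*Protocol*

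**What the plan says.** - **The decision set.** Protocol 16.1 states: "The ESP will be used to make decisions regarding escalation to higher veledimex doses for Arms 1 and 2 separately". Section 7.5 and SAP 4.4 base the recommended Phase II dose on the same set. On membership, Section 16.1 states: "The ESP will include subjects who received Ad-RTS-hIL-12 and at least one dose of their cohort specific-dose of veledimex after Ad-RTS-hIL-12 administration", and adds BSA conformance. The Synopsis, Section 14 and SAP 5.3 also use one dose as the threshold.
- **Adding subjects for under-exposure.** Section 16.1 provides only that "if at least one of three Ad-RTS-hIL-12 treated subjects does not receive at least one dose of veledimex, additional eligible subjects will be enrolled". The Synopsis has the same rule, specifying a dose after the injection.
- **Shortened courses.** Section 10.2 plans up to 14 doses in Arm 2. Section 7.6 and Table 6 hold study drug at a drug-related Grade 3 or higher event, and "The withheld doses will not be made up". Under Section 7.4, a related Grade 3 or higher non-hematologic event is a DLT only if it lasts at least 3 days.
- **Observation.** Section 7.1 says that the cohort decision "will occur after all dosed subjects in a cohort have been evaluated for at least 28 days". Section 7.3 has the SRC meet when the third or final subject completes the window. Section 8.5 says that subjects who withdraw between Day 0 and Day 28 "for reasons other than toxicity or disease progression may be replaced". Section 16.4.2 ends the safety evaluation period early for symptomatic deterioration, loss to follow-up, noncompliance or another reason, and then follows the child for survival only.
- **Counting.** Table 5 clears a level on 0 of 3, or on no more than 1 of 6, subjects with a DLT.

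**The concern.** A 3+3 count treats each child without a DLT as one full observation: the assigned dose was given and the child was watched for the whole window. The ESP requires neither. A child held in the first days for a related Grade 3 non-hematologic event that settles in under 3 days, and who never resumes, has no DLT under the definition, stays in the ESP and is not topped up. That child then helps to clear the dose, although the course was stopped for toxicity. A child who deteriorates and leaves before Day 28 without a recorded DLT can be counted in the same way.

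With three to six children per decision, one uninformative child matters. Clearance can open the 20 mg cohort or an expansion of up to 30 children. DLT occurrence is also part of the primary endpoint (Section 16.3.1), so the reported rate would be affected too.

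**Working it through.** **1. The plan's own figure.** The only sample-size figure is the total of 45. Cohort 1 closed at 3 (SAP 2.1.1), Cohorts 3 and 4 take at most 6 each, and the expansion takes 30: 3 + 6 + 6 + 30 = 45. It reproduces, with no slack. The plan states no 3+3 operating characteristics and no DLT rate.

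**2. Exposure threshold.** 1 / 14 = 7.1% of the Arm 2 course satisfies the ESP.

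**3. Effect on the 3+3.** Assumptions, none of them in the documents:
- the true 28-day DLT rate on a full course is p = 20%, one third, 40% or 50%;
- one of the first three children has risk f × p, with f = 0.5 (half the risk) or f = 0 (none);
- all other children carry the full risk p.

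P(clear) = q0 + q1 × r, where
- q0 = P(no DLT in the first three) = (1 − fp)(1 − p)²
- q1 = P(exactly one) = fp(1 − p)² + 2p(1 − p)(1 − fp)
- r = P(no DLT in the next three) = (1 − p)³

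Worked at p = 40%:
- f = 1: 0.216 + 0.432 × 0.216 = 0.309
- f = 0.5: 0.288 + 0.456 × 0.216 = 0.386
- f = 0: 0.360 + 0.480 × 0.216 = 0.464

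| True DLT rate | All three fully evaluable | One at half risk | One at no risk |
|---|---|---|---|
| 20% | 71% | 76% | 80% |
| One third | 43% | 50% | 58% |
| 40% | 31% | 39% | 46% |
| 50% | 17% | 24% | 31% |

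**4. Information in a clean cohort.** The one-sided 95% upper bound on the DLT rate after 0 of n is 1 − 0.05^(1/n). It is 63% for n = 3, and 78% if only two of the three are informative.

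**5. Observation, sections side by side.** Sections 7.1 and 7.3 set when the SRC decides. Section 8.5 makes replacement optional and does not provide for it after progression or toxicity. Section 16.4.2 lets safety evaluation stop before Day 28. None of them says whether an early leaver without a DLT is DLT-free, not evaluable or replaced.

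**The case against.** **The SRC is not bound by the count.** Section 16.2 lets it weigh other clinical factors, Section 7.2 has daily contact between investigator and Medical Monitor, Section 7.4 lets the Medical Monitor stop escalation before any DLT, and Section 7.10 holds enrollment after a death within 30 days of study therapy. A one-dose child would be known to those deciding. This stands, and it is why the point says such children can clear a level. It does not repair the count, which Section 16.2 presents as an independent algorithmic assessment.

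**Section 7.1 already requires 28 days on every dosed child, and Section 16.4.2 asks for three ESP subjects eligible for safety evaluation.** Both can be read as conditions beyond ESP membership. Neither defines eligibility nor says what happens to an early leaver.

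**SAP 5.3 removes some major deviations from the ESP.** That test concerns efficacy endpoints, SAP 8 says no subject is removed for a deviation, and deviations are finalised before database lock rather than at SRC meetings.

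**Stronger readings that a reader might infer, and that the documents do not support:**
- *Children leaving for documented progression are the main gap.* Section 8.4 lists confirmed progression as a reason to stop treatment, not to leave the study. Section 13.1 puts the confirming scan 4 weeks after first documentation. Table 1 requires Day 28 and Day 56 scans even with unconfirmed progression. The realistic early exits are symptomatic deterioration and withdrawn consent.
- *Sections 7.4 and 7.6 contradict each other on dose changes.* Section 7.4 says that if an expansion cohort "is implemented, the veledimex dose may be delayed or reduced for individual subjects in the event of toxicity". It does not say that this applies only there, and Section 7.6 is general. What is missing is a clear statement for the escalation window.
- *Two of three children could be uninformative.* At 40% with no remaining risk this gives 69%, but nothing in the documents suggests that frequency. Zero risk is itself an extreme, because every ESP child has been injected and local reactions can be DLTs.

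**Conclusion.** The concern holds in this form. For Arm 2 Cohorts 3 and 4 (Arm 1 closed with three subjects), the decision set has no minimum exposure beyond one post-injection dose, and no rule for counting a child who is not observed to Day 28. The exposure gap is firm on the text. The observation gap is narrower and comes from sections that have not been reconciled.

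One partly informative child among the first three raises the chance that the algorithm permits clearance by about 5 to 10 points at a true DLT rate of 20%, and by about 7 to 15 points at rates from one third to 50%. These figures rest on assumed DLT rates and an assumed risk fraction of 0 to 0.5. They describe what the 3+3 permits, not what the SRC would decide.

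**What to change.** 1. Add a DLT-evaluable set to Protocol 16.1 and SAP 5.3 and 11, and use it for every 3+3 count. A subject counts if he or she had a DLT in Day 0 to Day 28, or met a minimum exposure at the cohort dose, prespecified by the sponsor, and was observed to Day 28.
2. Change Section 8.5 so that subjects not evaluable for reasons other than toxicity, including early progression or deterioration without a DLT, will be replaced for the 3+3 count.
3. State that subjects who miss doses or leave because of study-drug toxicity short of a DLT are neither counted as DLT-free nor silently dropped. Dropping them could itself bias the DLT rate downwards. They are shown separately to the SRC before any escalation decision.
4. Reconcile Sections 7.1 and 7.3 with 8.5 and 16.4.2 on early leavers, and state whether the holds and reductions of Section 7.6 apply within the DLT window of an escalation cohort.

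**Cost.** Wording in both documents, and possibly one or two replacement subjects with a 28-day wait each. Because 3 + 6 + 6 + 30 already equals 45, a full enrollment has no room for them. They would have to rely on the approximate total in Section 8.3, a smaller expansion or a slightly restated ceiling.

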16.2. Sample Size and Power Calculations

- The sample size chosen was based on clinical considerations.

- For Cohorts 1 and 3, treated at 10 mg, the 3+3 rule-based dose escalation criteria will be applied to provide an independent algorithmic safety assessment to either dose escalate from 10 to 20 mg or to consider de-escalation, as applicable. The SRC will incorporate the findings in combination with other clinical factors to make the final recommendation pertaining to dose escalation from 10 mg to 20 mg or de-escalation from 10 mg to 5 mg.
- For Cohort 4, treated at 20 mg, the 3+3 rule-based dose escalation criteria will be applied to provide an independent algorithmic safety assessment to either confirm that 20 mg dosing is safe or to potentially de-escalate to a 15 mg dose for further evaluation based on the SRC recommendation.

After the dose escalation/de-escalation portion of the study Phase II dose will be determined for both pediatric disease populations:

- recurrent or refractory supratentorial brain tumor pediatric population
- DIPG pediatric population

At the discretion of the SRC, up to 30 evaluable DIPG subjects may be enrolled in the Phase II expansion cohort, which will support time to OS estimation. The projection of this sample size is based on clinical considerations as well as numbers to obtain sufficient preliminary assessments of overall response. Additional details will be provided in the Statistical Analysis Plan.

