In addition to recommending dose escalation, cohort expansion, or discontinuation of treatment, as noted above, the SRC may recommend dose de-escalation at any point based on safety review.

Dose De-Escalation

If it is determined that dose escalation or cohort expansion should not proceed, dose de-escalation may be undertaken and the SRC will consider de-escalating the veledimex dose as follows:

- De-escalation by increments of 5 mg from the cohort in which 2 or more DLTs were observed (*e.g.*, 15 mg, de-escalated from 20 mg)
- If there are 2 or more DLTs in the dose de-escalation cohort, the SRC will consider stopping enrollment at that dose and de-escalating the veledimex dose by an additional increment of 5 mg (*e.g.*, 5 mg down from 10 mg) or declaring a previously studied dose level the recommended Phase II pediatric dose

If no DLTs occur among the three subjects in Cohort 1, dosing may proceed to the next cohort, Cohort 3, after the SRC provides their recommendation to proceed (Table 5). In any cohort, if one DLT occurs among the three subjects, three additional subjects will be enrolled. If one or more of the three additional subjects experience a DLT, dosing will stop. The SRC will then convene to evaluate safety, determine if the recommended Phase II dose has been reached per **Section 7.5**, and will decide whether to stop treatment or de-escalate veledimex dosing. The SRC may also seek an *ad hoc* safety evaluation and recommendation by external experts as needed.

Table 5: Dose Escalation and De-Escalation Decision Rules

Subjects with DLTs (Any Dose Level)	Decision Rule	Subject Count
None of the first 3 subjects OR ≤ 1 subject (in the case of a 6-patient cohort) experiences a DLT	Expand current dose level cohort or enroll the next higher dose level cohort (after SRC recommendation).	3 or 6
1 of the first 3 subjects experiences a DLT	Enroll at least 3 more subjects in this dose level cohort. If none of the 3 additional subjects experiences a DLT, expand current dose level cohort or proceed to the next planned dose level cohort (after SRC recommendation).	6

Table 5: Dose Escalation and De-Escalation Decision Rules (Continued)

Subjects with DLTs (Any Dose Level)	Decision Rule	Subject Count

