16.3. Endpoints

16.3.1. Primary Endpoint

- The primary endpoint is the assessment of safety and tolerability of Ad-RTS-hIL12, administered by intratumoral injection plus veledimex administered PO, as determined by the AE rate and the occurrence of DLTs analyzed specifically for each cohort.

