#### **11. DOSE LIMITING TOXICITIES (DLT)**

In general, listings by subject ID for DLT data by treatment arm and dose cohort, will be provided for the ESP.

The number of DLTs and the proportion of subjects with any DLT and each type of DLT will be summarized by treatment arm and dose cohort for the ESP if applicable.

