### **14.2. Objective Response Rate (ORR)**

ORR is the proportion of subjects meeting iRANO response criteria which is defined as sum of partial responses plus complete responses. ORR will be summarized using frequency tables by arm and dose cohort, and visit with 2-sided 95% exact binomial confidence interval (CI).

A figure similarly to a forest plot will be provided to display the response rates of each arm and dose cohort systematically along with a 2-sided 95% exact binomial confidence CI.

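### Protocol Section 16.2 says the Cohort 4 3+3 rule can confirm that 20 mg is safe; 3 to 6 subjects cannot support that, and SAP Section 11 gives the DLT proportion no interval

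*Protocol*

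**What the plan says.** Protocol Section 16.2 states that "The sample size chosen was based on clinical considerations" and gives no error rate or operating characteristic. It then assigns the 3+3 rule a purpose in each cohort. For Cohorts 1 and 3 (10 mg) the rule informs whether to escalate or consider de-escalation. For Cohort 4 the purpose is an "algorithmic safety assessment to either confirm that 20 mg dosing is safe or to potentially de-escalate to a 15 mg dose", with further evaluation resting on the SRC's recommendation. Within the plan 20 mg is the highest dose, so no later cohort tests it further.

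The favourable row of Table 5 (Protocol Section 7.3) reads "None of the first 3 subjects OR ≤ 1 subject (in the case of a 6-patient cohort) experiences a DLT". The path to six subjects is sequential: "In any cohort, if one DLT occurs among the three subjects, three additional subjects will be enrolled". Then: "If one or more of the three additional subjects experience a DLT, dosing will stop".

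The primary endpoint (Protocol Section 16.3.1) is safety and tolerability "as determined by the AE rate and the occurrence of DLTs analyzed specifically for each cohort". For its DLT part, SAP Section 11 plans subject listings for the ESP and adds, if applicable, "The number of DLTs and the proportion of subjects with any DLT and each type of DLT will be summarized" by arm and dose cohort. Neither document plans an interval for that proportion. SAP Section 14.2 does plan a two-sided 95% exact binomial interval for ORR, a secondary endpoint, by the same arms and dose cohorts.

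**The concern.** The 3+3 rule is a screen for whether to go on. Seeing few DLTs in 3 to 6 subjects means that a stopping criterion was not met; it does not show that the DLT rate is low. Section 16.2 attaches the stronger conclusion to the weaker evidence, and only for the top dose.

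Safety and tolerability is the primary objective, and the same 3-to-6-subject result can open an expansion of up to 30 children. If the Section 16.2 wording carried into a report, a result such as 0/3 could be described as confirming safety while a DLT rate near 60% remained compatible with the data. A DLT table that gives a proportion of 0% with no interval would not correct that impression.

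**Working it through.** The plan states no operating characteristic, so there is no figure of its own to reproduce.

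**Inputs.** Clearing rule: 0/3, or 1/3 followed by 0/3 (Protocol Section 7.3 and Table 5). Cohort size: 3 to 6 (Protocol synopsis, sample size). Reference DLT rate: 33%, from the definition of the recommended Phase II dose (Protocol Section 7.5, SAP Section 4.4). Subjects are taken as independent, enrolled 3 then 3, with no SRC override.

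**Step 1. Probability that the algorithm clears a dose with true DLT rate p.**

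P(clear) = (1−p)³ + 3p(1−p)² × (1−p)³

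At p = 0.33: 0.3008 + 0.1337 = 0.434. At p = 1/3: 0.2963 + 0.1317 = 0.428. Both round to 43%.

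| True DLT rate | P(clear) |
|---|---|
| 10% | 0.906 |
| 20% | 0.709 |
| 25% | 0.600 |
| 30% | 0.494 |
| 33% | 0.434 |
| 40% | 0.309 |
| 50% | 0.172 |

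P(clear) falls to 0.20 only at a true rate of about 48% (p = 0.476).

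**Step 2. What the clearing results exclude (exact binomial, Clopper-Pearson).**

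- 0/3: solve (1−p)³ = 0.05, so p = 1 − 0.05^(1/3) = 0.632. Two-sided 95% interval: 0 to 70.8%.
- 1/6: solve (1−p)⁶ + 6p(1−p)⁵ = 0.05, so p = 0.582. Two-sided 95% interval: 0.4% to 64.1%.
- 0/6: p = 1 − 0.05^(1/6) = 0.393. The Section 7.3 path does not reach this result, because three more subjects are added only after a DLT. It is shown as the best that six subjects could give.

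**Step 3. Smallest DLT-free sample with a one-sided 95% upper bound below 33%.** ln(0.05)/ln(0.67) = 7.48, so 8 subjects. That exceeds the six-subject maximum, so no result within the planned cohort size excludes 33%.

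**Step 4. The later check.** Protocol Section 7.4 lets the SRC turn to a lower or intermediate dose if at least 33% of expansion subjects have DLTs. With 30 subjects that means at least 10. The probability of reaching 10 is 0.553 at a true rate of 33% and 0.568 at 1/3. The check is discretionary, and no interval is planned there either.

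**The case against.** The best case for leaving the plan alone has four parts.

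*The SRC decides.* The algorithm is one input, and expansion follows only on the SRC's recommendation. This stands as a limit on the 43%. A reader might take 43% as the chance that children go on at 20 mg when the true rate is 33%. The documents do not support that, because the figure describes the algorithm alone. Discretion also runs both ways: Table 5 allows the SRC to recommend continuing at the existing dose after 2 DLTs.

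*The 33% is not a target true rate.* This is correct. A reader might infer that the protocol names 33% as an unacceptable true rate that the data must exclude. Section 7.5 states a rule on the observed proportion within a cohort and sets no margin or hypothesis. The value is used here only as a reference point.

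*Small-sample summaries are deliberately avoided.* SAP Section 6.1 prefers listings, SAP Section 11 puts listings first, and the protocol synopsis reduces ORR and PFS to listings if no expansion is run. That weakens the contrast with ORR and means three subjects will be visible as three. It does not remove the gap: SAP Section 11 still provides for a DLT proportion, and SAP Section 14.2 still plans exact intervals for ORR by dose cohort.

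*Other safeguards exist.* Section 7.10 pauses enrolment for specified events, Section 7.2 requires daily contact with the Medical Monitor before dosing, and Section 7.4 sets the expansion check. These soften the harm. None supplies a bound on the DLT rate or makes the Cohort 4 rule confirmatory.

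**Conclusion.** The point holds as one of wording and reporting. Section 16.2 gives the Cohort 4 rule a confirmatory property that it lacks. The algorithm clears a true DLT rate of 33% about 43% of the time, the one-sided 95% upper bounds at the clearing results are 63% and 58%, and even 0/6 would leave 39%. The proportion planned in SAP Section 11 carries nothing to show this.

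The figures rest on independent subjects, the sequence of 3 then 3, no SRC override and, for the 1/6 bound, treating six as a fixed sample size.

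Three stronger readings go too far. A reader might infer that the trial will report 20 mg as confirmed safe. The phrase stands only in the sample-size section, and the primary endpoint is descriptive. A reader might infer that a bound below 33% needs the full expansion. It does not: 0/8 gives 31% and 1/13 gives 32%. A reader might also want every safety statement tested against a 33% bound. Nothing in the documents sets such a test, and it would be a demanding one: at most 6 DLTs in 33 subjects (or in 36) would be met only 50% (or 40%) of the time at a true rate of 20%.

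**What to change.** 1. In Protocol Section 16.2, replace the statement that the rule confirms 20 mg dosing as safe with one saying that the 20 mg level did not meet the dose-escalation stopping criterion. Add that this result does not establish a DLT rate below 33%.

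2. In SAP Section 11, wherever the DLT proportion is summarised, give a two-sided exact binomial 95% interval by dose cohort, using the method in SAP Section 14.2. If an expansion is run, give it also for all DLT-evaluable subjects at the same dose. Present it as a descriptive statistic beside the subject listings, with no pass mark attached.

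The cost is a short rewording in Section 16.2 and one added statistic in the DLT summary. No subjects, visits or procedures are added, and the escalation rule and the SRC's role do not change. The downside is presentational: 0/3 would appear with an interval of 0 to 71%, and 1/6 with 0.4% to 64%. That width is what the data support.
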